5.2.2. Prior/Concomitant therapy

- Use of any investigational or non-registered product (drug or vaccine) other than the study interventions during the period beginning 30 days before the first dose of study intervention or their planned use during the study period. EXC#11

- Planned administration/administration of a vaccine not foreseen by the study protocol in the period starting 30 days before each dose and ending 30 days after each dose of study intervention administration with the exception of influenza vaccine (pandemic or seasonal). EXC#12
- A vaccine not foreseen by the study protocol administered during the period starting at Visit 1 or 30 days before each dose and ending 30 days after the last dose of study intervention administration*, with the exception of influenza vaccine (pandemic or seasonal). EXC#13

*In case emergency mass vaccination for an unforeseen public health threat (e.g., a pandemic) is organized by public health authorities outside the routine immunization program, the time period described above can be reduced if necessary for that vaccine, provided it is licensed/authorized and used according to its Product Information.

- Administration of long-acting immune-modifying drugs at any time during the study period (e.g., infliximab). EXC#14
- Chronic administration (defined as more than 14 days in total) of immunosuppressants or other immune-modifying drugs during the period starting 3 months before the first study intervention dose(s). For corticosteroids, this will mean prednisone equivalent ≥ 20 mg/day. Inhaled and topical steroids are allowed. EXC#15
- Administration of immunoglobulins and/or any blood products or plasma derivatives during the period starting 3 months before the administration of the first dose of study intervention or planned administration during the study period. EXC#16

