6.9. Concomitant therapy

At each study visit/contact the investigator or his/her delegate should question the participant about all medications/products taken, and vaccinations received by the participant.

The following concomitant medication(s)/product(s)/vaccine(s) must be recorded in the eCRF:

- All concomitant medication associated with an adverse event, including vaccines/products, except vitamins and dietary supplements, administered during a 31-day follow-up after each dose of study intervention (i.e., day of vaccination and 30 subsequent days).
- All concomitant medication leading to discontinuation of the study intervention or elimination from the analysis, including products/vaccines. Please refer to Sections [5.2.2](#) and [9.2.1](#) for further details.

- All concomitant medication which may explain/cause/be used to treat an SAE/pIMD including vaccines/products, as defined in Sections [8.4.1](#) and [10.3.2](#). These must also be recorded in the Expedited Adverse Event Report.

The LML should be contacted if there are any questions regarding concomitant or prior therapy.

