### ***Secondary estimand***

The secondary clinical question of interest is to assess the humoral immune response in all eligible participants who received all doses as per protocol, had immunogenicity results post-dose, complied with dosing/blood draw intervals, without intercurrent conditions that may interfere with immunogenicity and without prohibited concomitant medication/vaccination (i.e., the Per Protocol Set [PPS]).

The estimand is described by the following attributes:

- Population: PPS. If in any study group, the percentage of vaccinated participants with serological results excluded from the PPS is more than 10%, a second analysis based on the ES will be performed to complement the PPS analysis.
- Treatment condition: 5 treatment groups as described in [Table 1](#).
- Variable / endpoint:
  - Anti-hepatitis B surface antigen (HBs) antibody (Ab) concentrations at Day 1, Day 31, Day 61 and Day 361.
  - Anti-HBs seroconversion and seroprotection status at Day 31, Day 61 and Day 361.
- Summary measure:
  - Geometric Mean Concentrations (GMC) of Anti-HBs Ab.
  - Percentage of participants above seroconversion and seroprotection thresholds.
    - Participants not having results for a specific visit (but being part of the PPS) will not be considered in the denominator, no imputation will be done (see Section [6.3.2](#) for details).

[figure not shown]
CCI

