**Table 4 List of elimination codes**

Code	Condition under which the code is used	Visit when it is applicable	Applicable for analysis set/endpoint
800	Fraudulent data	All	Enrolled set, ES and PPS, CCI
900	Invalid informed consent	All	Enrolled set, ES and PPS, CCI
1030	Study intervention not administered at all, but participant number allocated	All	ES, PPS, CCI
1040	Administration of concomitant vaccine(s) forbidden in the protocol: 
 
Use of any investigational or non-registered vaccine other than the study interventions during the period beginning 30 days before the first dose of study intervention, or their planned use during the study period.
 
Planned administration/administration of a vaccine* not foreseen by the Protocol in the period starting 30 days* before each dose and ending 30 days* after each dose of study intervention administration**.               
With the exception of influenza vaccine (pandemic or seasonal).
 
**In case an emergency mass vaccination for an unforeseen public health threat (e.g., a pandemic) is recommended and/or organized by public health authorities outside the routine immunization program, the time period described above can be reduced if, necessary for that vaccine, provided it is used according to the local governmental recommendations and that the Sponsor is notified accordingly.
 
 
	From the specific visit the condition is met	ES, PPS, CCI
1050	Randomization failure: Participant not treated according to regimen assigned by randomization	From the specific visit (1, 4 or 8) the condition is met	PPS and CCI
1070	Vaccine administration not according to protocol Incomplete vaccination course Participant was vaccinated with the correct vaccine but containing a lower volume Wrong replacement or study vaccine administered (not compatible with the vaccine regimen associated to the treatment number) Route of the study vaccine is not intramuscular Wrong reconstitution of administered vaccine	From the specific visit (1, 4 or 8) the condition is met and from the specific visit (1 or 4) the condition is met but only up until the visit before the next dose for CCI	PPS, CCI

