2080	Participants did not comply with vaccination schedule: 
 
Number of days between Visit 1 and Visit 4 is outside [21-42 days] for all study groups
 
Number of days between Visit 4 and Visit 8 is outside [136-164 days], for HBs-alum group
 
	From the specific visit the condition is met.	PPS
2090	Participants did not comply with blood sample schedule (any of the below options): 
 
Number of days between Visit 1 and Visit 4 is outside [21-42] days
 
Number of days between Visit 4 and Visit 7 is outside [21-42 days]
 
Number of days between Visit 7 and Visit 9 is outside [286-314 days]
 
	At the specific visit (4 or 7 or 9) the condition is met	PPS
2100	Serological antibody results not available.	At the specific visit (1 or 4 or 7 or 9) the condition is met	PPS

Code	Condition under which the code is used	Visit when it is applicable	Applicable for analysis set/endpoint
2110	Blood sample for serological antibodies available but not yet tested (main analysis)	At the specific visit (1, or 4, or 7, or 9) the condition is met	PPS
2120	Issues in the lab results that are not related to handling of lab samples (Eg: Hemolysis, calibration of instruments) Unreliable released data as a result of confirmed sample mismatch or confirmed inappropriate sample handling at lab	At the specific visit the condition is met	PPS

CCI

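### An outside hepatitis B vaccine triggers no mandatory PPS elimination after about Day 61 in the two-dose groups or Day 211 in HBs-alum, so Day 361 anti-HBs results can include participants boosted off study

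*SAP*

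**What the plan says.** Three rules reach a licensed vaccine that is not part of the study, and each is tied to a study dose.

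- SAP Table 4, code 1040: elimination for an unforeseen vaccine given "in the period starting 30 days* before each dose and ending 30 days* after each dose of study intervention administration", influenza vaccine excepted.
- Protocol 5.2.2, EXC#12: the same window, "in the period starting 30 days before each dose and ending 30 days after each dose of study intervention administration".
- Protocol 5.2.2, EXC#13: one continuous window, "during the period starting at Visit 1 or 30 days before each dose and ending 30 days after the last dose of study intervention".

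A fourth rule, EXC#11, runs through the whole study but covers only "Use of any investigational or non-registered product (drug or vaccine) other than the study interventions".

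Four groups (HBs-AS03, HBs-AS04, HBs-AS37_50, HBs-AS37_100) are dosed at Visits 1 and 4. HBs-alum is also dosed at Visit 8, and code 2080 checks the timing of that dose: "Number of days between Visit 4 and Visit 8 is outside [136-164 days], for HBs-alum group".

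The SAP's secondary estimand is defined on the PPS. Its variables are anti-HBs concentration, with Day 361 among the timepoints, and "Anti-HBs seroconversion and seroprotection status at Day 31, Day 61 and Day 361". The PPS definition removes participants who received prohibited vaccinations, not every vaccination that could affect the result.

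**The concern.** The Day 361 sample is taken about 300 days after the dose-linked bar closes in the two-dose groups. A participant who receives a licensed hepatitis B-containing vaccine in that time is re-exposed to the antigen whose antibody is being measured. Followed to the letter, the elimination codes keep that participant in the Day 361 PPS, and the result counts towards the study regimen.

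The plan does protect this sample in other respects. Code 2040 eliminates participants given immunoglobulins, blood products or long-acting immune-modifying drugs during the study period. No reason is given for guarding against those and not against a further dose of the antigen.

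The gap also differs by group. HBs-alum is covered for longer than the other four groups, including both AS37 groups.

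**Working it through.** The plan states no figure on this point, so there is none to reproduce. The check has three parts.

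**1. When the bar ends.** Nominal dose days are Day 1, Day 31 and, for HBs-alum only, Day 181.

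| Group and rule | Bar ends | Days open before the Day 361 sample |
|---|---|---|
| Two-dose groups, any of the three rules | 31 + 30 = Day 61 | Days 62–360: 360 − 61 = 299 |
| HBs-alum, EXC#13 with code 2010 | 181 + 30 = Day 211 | Days 212–360: 360 − 211 = 149 |
| HBs-alum, code 1040 alone | Day 61, resuming from 181 − 30 = Day 151 to Day 211 | Days 62–150 (150 − 61 = 89), plus the same 149 |

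The allowed visit intervals move these dates. Visit 4 can fall on Day 22 to 43 (1 + 21 to 1 + 42), so the two-dose bar ends between Day 52 and Day 73. Visit 8 can fall on Day 158 to 207 (22 + 136 to 43 + 164), so the HBs-alum bar ends between Day 188 and Day 237.

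**2. Whether another code closes the gap.** SAP 3.1.3 lists the codes that remove a participant from the PPS.

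- Code 2010 covers breaches of the inclusion and exclusion criteria and removes the participant at all visits. Through EXC#13 it closes Days 62–150 in HBs-alum. It adds nothing after Day 61 in the two-dose groups, because EXC#13 has ended there.
- EXC#1 concerns earlier hepatitis B vaccination and is checked at entry.
- Code 2040 and EXC#11 reach investigational or non-registered products, not a licensed vaccine.
- Code 2050 is headed as an intercurrent medical condition, is worded as optional, and does not mention vaccination.
- The complementary analysis on the Exposed Set would also keep the participant.

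**3. Possible size (illustration only).** If m of n participants have a Day 361 concentration k times the unboosted value, the group GMC is multiplied by k^(m/n). Each such participant can move a seroprotection rate by up to 1/n, but only if otherwise below threshold. The values of k and m are assumed; n is the planned 23 to 30.

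| n | m | k = 10 | k = 100 | Largest shift in rate (m/n) |
|---|---|---|---|---|
| 23 | 1 | 1.105 | 1.222 | 4.3 points |
| 23 | 2 | 1.222 | 1.492 | 8.7 points |
| 30 | 1 | 1.080 | 1.166 | 3.3 points |
| 30 | 2 | 1.166 | 1.359 | 6.7 points |

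The chance of at least one boosted participant is 1 − (1 − p)^n. For an assumed uptake p of 1%, 2% or 5%, it is 21%, 37% or 69% in a group of 23. Across the four two-dose groups (4 × 23 = 92) it is 60%, 84% or 99%.

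**The case against.** **Recording.** A reader might infer that outside doses would mostly go unrecorded, because protocol 6.9 limits its first recording item to medication associated with an adverse event and "administered during a 31-day follow-up after each dose of study intervention (i.e., day of vaccination and 30 subsequent days". The documents do not support that. Section 6.9 opens by requiring participants to be asked about vaccinations at every visit or contact. The Schedule of Activities row for concomitant medications and vaccinations carries the eCRF-required symbol at every contact through Visit 9. SAP 4.2.1 lists participants with concurrent vaccines. What remains is a mismatch between the 6.9 list and that row.

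**Discretion.** Protocol 9.2.1 allows PPS elimination for criteria in 7.1.1, which refers back to 5.2.1 and so to EXC#1. Code 2050 allows it for a confirmed change in immune status. A recorded outside dose could therefore be eliminated, and retention is not forced. But both routes are optional. Section 7.1.1 governs further study doses, and the two-dose groups have none after Day 31. Nor can EXC#1 serve as a continuing test when every participant receives HBsAg in the study. In an open-label trial, case-by-case removal is a weak substitute for a rule.

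**Consequence.** The analyses are descriptive, and protocol 9.3.2 specifies pairwise comparisons post-Dose 1 and Dose 2 without naming Day 361. The third dose already makes HBs-alum differ from the other groups at Day 361 by design. With an assumed log10 SD of 0.4 to 0.8, the 95% CI at n=23 spans a factor of about 1.5 to 2.2 either side of the GMC, so one boosted participant lies well inside it. All of this stands and limits the weight of the point, but it does not make the rule complete.

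**Conclusion.** The gap is real in a bounded form. A licensed outside hepatitis B-containing vaccine triggers no mandatory PPS elimination after about Day 61 in the two-dose groups and after about Day 211 in HBs-alum. The Day 361 PPS results can include participants boosted off study, and the protection is unequal between HBs-alum and the other groups.

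Two stronger readings fail. The gap does not open at Day 61 in every group, because EXC#13 with code 2010 covers HBs-alum to about Day 211. Nor do the documents show that uptake would differ by group. The open-label design makes that conceivable, but nothing in the text measures it.

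The effect falls on a secondary, descriptive endpoint. The Day 61 main analysis is unaffected, since at nominal visit days the bar runs up to that sample. The illustrative GMC increase from one boosted participant (11–22% at n=23, 8–17% at n=30) rests wholly on assumed fold-rises, and the number boosted is unknown. Redacted text could hold a further rule, but none is visible. A one-line correction before the Day 361 analysis is worthwhile.

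**What to change.** 1. In SAP Table 4, add to code 1040, for the PPS only: administration of any non-study hepatitis B-containing vaccine from Visit 1 to Visit 9, with elimination from the next visit onwards. State the PPS restriction explicitly, because the existing 1040 row also names the Exposed Set. This is an analysis rule and does not change what participants may receive.
2. Align the code 1040 window with EXC#13, so that HBs-alum Days 62–150 do not depend on code 2010 alone. State which code governs, since 2010 removes a participant at all visits and 1040 only from the visit concerned.
3. Identify such doses from the vaccination records that the Schedule of Activities already requires through Visit 9, and reconcile the narrower list in protocol 6.9 with that row.

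The cost is one line in the SAP and a clarification in protocol 6.9, with no new data collection. A participant or two may leave the Day 361 PPS.

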Return of eDiary devices or removal of eDiary application from participant personal device																		○			
Recording of unsolicited events (Days 1-31) post-Dose 1 and post-Dose 2 of study intervention administration		●	●	●	●	●	●	●	●	●	●	●	●	●	●	●	●	●	●	See Section 10.3.8 for more information	
Recording of SAEs, MAEs, pIMDs and pregnancies		●	●	●	●	●	●	●	●	●	●	●	●	●	●	●	●	●	●	See Section 10.3.8 for more information	
Recording of SAEs related to study participation, or to a concurrent GSK medication/vaccine	●	●	●	●	●	●	●	●	●	●	●	●	●	●	●	●	●	●	●	See Section 10.3.8 for more information	
Recording of AEs/SAEs leading to withdrawal from the study		●	●	●	●	●	●	●	●	●	●	●	●	●	●	●	●	●	●	See Section 10.3.8 for more information	
Study Conclusion																				●	See Section 4.5 for more information

V = visit; PC = phone contact; D = day; HBs = Hepatitis B surface antigen; HBc = Hepatitis B core antigen; CMI = cell-mediated immunity; eDiary = electronic diary; SAE = serious adverse event; MAE = medically attended event; pIMD = potential immune-mediated disorder; AE = adverse event; eCRF = electronic case record form; CCI [REDACTED]

CCI [REDACTED].

Note: The double-line border following Day 61 indicates the main analyses that will be performed on all data (i.e., data that are as clean as possible) obtained up to Day 61.

● is used to indicate a study procedure that requires documentation in the individual eCRF.

○ is used to indicate a study procedure that does not require documentation in the individual eCRF.

CONFIDENTIAL

215301 (EARLY-CLINRES-017)
Protocol Amendment 4 Final

1Only for participants in the HBs-alum group.

2Note: Participants with anti-HBs Ab concentration < 100 mIU/mL at Day 361 will be offered a dose of *Engerix-B* after the study.

CCI

[figure not shown]

Table 2 Intervals between study visits

Interval	Optimal length of interval ¹	Allowed interval ²
Screening Visit → Visit 1	7 days	2-28 days
Visit 1 → Visit 2*	1 day	1 day
Visit 2 → PC1	2 days	2 days
PC1 → PC2	2 days	2 days
Visit 1 → Visit 3	7 days	7-8 days
Visit 3 → PC3	2 days	2 days
PC3 → PC4	2 days	2 days
PC4 → PC5	3 days	3 days
Visit 1 → Visit 4	30 days (1 month)	21-42 days
Visit 4 → Visit 5*	1 day	1 day
Visit 5 → PC6	2 days	2 days
PC6 → PC7	2 days	2 days
Visit 4 → Visit 6	7 days	7-8 days
Visit 4 → Visit 7	30 days (1 month)	21-42 days
Visit 4 → Visit 8 ³	150 days (5 months)	136-164 days
Visit 6 → PC8	2 days	2 days
PC8 → PC9	2 days	2 days
PC9 → PC10	3 days	3 days

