#### **3.1.3. Elimination from Per-protocol Set (PPS)**

A participant will be excluded from the per-protocol set (PPS) for analysis of humoral immunogenicity in the following manner:

- For codes 800, 900, 1030, 1050 and 2010: participants will be eliminated for all visits.
- For codes 1040, 1070, 1080, 1090, 2040, 2050 and 2080: participants will be eliminated from the specific visit at which the condition is met and onwards.
- For codes 2090, 2100, 2110, 2120: participants will be eliminated at the specific visit at which the condition is met.

CCI

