## 4.8. Changes to Protocol- Defined Analyses

Not applicable.

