## 5. SAMPLE SIZE DETERMINATION

A minimum of 23 (and maximum of 30) participants per group will be enrolled in this study. The target sample size has been reduced from 30 to 23 participants per group for reasons of feasibility, as discussed in Section 4.2.1 of the study protocol. [redacted]

[redacted]  
[redacted]  
[redacted]  
[redacted]  
[redacted].

The sample size is not based on formal hypothesis testing and is typical for this kind of study where a treatment is tested for the first-time in human. [redacted]

[redacted]  
[redacted]  
[redacted]  
[redacted]

The primary objectives of the study are to assess the reactogenicity and safety of each vaccine dose throughout the study. [redacted]

[redacted]  
[redacted]  
[redacted].

[figure not shown]
[redacted]  
[redacted]  
[redacted]

[redacted]

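### SAP elimination code 2090 judges the HBs-alum Day 361 sample by a visit window that Protocol Table 2 reserves for the other four groups, and never checks the HBs-alum window

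*SAP*

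**What the plan says.** Protocol Section 1.3, Table 2 sets the Visit 9 window by group. Visit 7 to Visit 9 is allowed 286-314 days, and footnote 4 limits that row to groups other than HBs-alum. Visit 8 to Visit 9 is allowed 166-194 days, and footnote 3 limits that row to HBs-alum. Footnote 2 makes the allowed intervals a condition of entry to the per-protocol set (PPS) for immunogenicity.

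SAP Table 4 implements the blood-sample windows through code 2090, introduced as "Participants did not comply with blood sample schedule (any of the below options". Its three options are Visit 1 to Visit 4, Visit 4 to Visit 7, and "Number of days between Visit 7 and Visit 9 is outside [286-314 days". None names a group, and Visit 8 to Visit 9 does not appear. The code just above it, 2080, does separate the control group: "Number of days between Visit 4 and Visit 8 is outside [136-164 days], for HBs-alum group".

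SAP Section 3.1.3 gives the consequence: "For codes 2090, 2100, 2110, 2120: participants will be eliminated at the specific visit at which the condition is met". SAP Section 4.8, headed "Changes to Protocol- Defined Analyses", is marked not applicable, so the SAP declares no departure from the protocol.

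**The concern.** HBs-alum is the only group dosed at Visit 8, so its Day 361 sample is taken after Dose 3. The protocol therefore times that sample from Visit 8. The SAP times it from Visit 7, a visit at which no dose is given, and does not enforce the interval from the last dose.

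Two errors follow for HBs-alum at Visit 9. A participant who met every protocol interval can be excluded, and one whose Visit 8 to Visit 9 interval is outside the protocol's limits can be kept. The Day 361 GMC, seroconversion and seroprotection results for the licensed-vaccine control would then come from a population other than the one the protocol defines, while the other four groups follow their own protocol window.

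**Working it through.** **Inputs (Protocol Table 2).**

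| Interval | Optimal (days) | Allowed (days) | Applies to |
|---|---|---|---|
| Visit 4 to Visit 7 | 30 | 21-42 | all groups |
| Visit 4 to Visit 8 | 150 | 136-164 | HBs-alum |
| Visit 8 to Visit 9 | 180 | 166-194 | HBs-alum |
| Visit 7 to Visit 9 | 300 | 286-314 | all except HBs-alum |

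**Identity for HBs-alum.** (V7-V9) = (V4-V8) + (V8-V9) - (V4-V7).

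**Optimal schedule.** 150 + 180 - 30 = 300 days, which matches the protocol's optimal Visit 7 to Visit 9 interval. The two rules agree when every visit is on its planned day and diverge only when visits drift.

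**Range for a compliant HBs-alum participant.** Shortest: 136 + 166 - 42 = 260 days. Longest: 164 + 194 - 21 = 337 days. Code 2090 accepts 286-314.

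**Compliant but dropped.** V4-V7 30, V4-V8 158 and V8-V9 187 are all allowed. 158 + 187 - 30 = 315, so code 2090 excludes the participant.

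**Non-compliant but kept.** V4-V7 30 and V4-V8 136 are allowed, but V8-V9 200 exceeds 194. 136 + 200 - 30 = 306, so code 2090 passes the participant.

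**What the SAP does enforce on time since Dose 3.** Codes 2080 and 2090 together bound V8-V9 at 286 + 21 - 164 = 143 to 314 + 42 - 136 = 220 days, against the protocol's 166-194.

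**Enumeration.** The allowed whole days give 22 × 29 × 29 = 18,502 compliant combinations. Of these, 3,256 fall below 286 and 2,299 above 314: 5,555 / 18,502 = 30.0%. This weights every allowed day equally. It is illustrative and not an upper bound.

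**Simulation.** The documents give no visit scatter, so the SD is assumed. Days are rounded and the other windows are met. Model A draws the three HBs-alum intervals as independent normals around 30, 150 and 180 days. Model B scatters Visits 7, 8 and 9 independently around days 30, 150 and 330 from Visit 4, as if booked to fixed dates.

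| SD (days) | Compliant but dropped, A / B | Non-compliant among retained, A / B |
|---|---|---|
| 3 | 0.5% / 0.05% | 0.0% / 0.06% |
| 5 | 8.1% / 2.5% | 0.2% / 3.3% |
| 7 | 16.5% / 7.3% | 1.8% / 9.7% |
| 10 | 23.1% / 13.9% | 7.1% / 17.2% |

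At SD 5 the expected number wrongly dropped is 23 × 0.025 = 0.6 to 23 × 0.081 = 1.9, or 30 × 0.025 = 0.8 to 30 × 0.081 = 2.4.

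**Is the check elsewhere?** SAP Section 3.1.3 lists 16 codes that eliminate from the humoral PPS. All 16 are readable in Table 4, and none tests Visit 8 to Visit 9, so redaction does not account for the gap. The special-circumstances extension in Protocol Section 8 covers only Visit 1 to Visit 4 and Visit 4 to Visit 7.

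**The case against.** The strongest reply is that little depends on this. It touches one group at one post-dose timepoint, for a secondary endpoint in a study that is descriptive throughout. Code 2090 acts only at the visit concerned, so Day 31, Day 61 and the main analysis are untouched. The pairwise comparisons in Protocol Section 9.3.2 are described for post-Dose 1 and post-Dose 2, so the readable text does not clearly plan a between-group comparison of the affected data. Nothing in the documents links visit timing to immune response, so no shift in a Day 361 result has been shown. If sites keep close to plan (SD 3 days), at most about 0.5% of compliant participants are dropped.

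All of that stands as a limit on the consequence, and the rates are assumptions. None of it removes the contradiction, which depends on no rate. Elimination codes exist for visits that drift, and that is where this one goes wrong.

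The supplementary Exposed Set analysis is a partial safeguard. The SAP triggers it when more than 10% are excluded in a group: 3 of 23 (13.0%) or 4 of 30 (13.3%). Protocol Section 9.3.2 sets 5% or more at one timepoint which, if read per group, is 2 of 23 (8.7%) or 2 of 30 (6.7%). Exclusions for other reasons also count. Wrong exclusions alone would reach 3 of 23 with probability of about 28% (Model A) or 2% (Model B) at SD 5, and about 76% or 23% at SD 7. The safeguard may therefore operate, but it complements the PPS result without correcting it, and participants wrongly kept add nothing towards either trigger.

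**Conclusion.** The concern holds. Code 2090 contradicts Protocol Table 2 for HBs-alum at Visit 9, and following it as written misclassifies participants in both directions. It reads as an oversight: code 2080 handles the same group separately, and SAP Section 4.8 declares no change.

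The window arithmetic (260-337 days for compliant participants, 143-220 days for the enforced time since Dose 3) is exact. How many participants are affected depends on unknown visit scatter: practically none at SD 3 days, one or two of 23-30 at SD 5, more if timing is looser. The damage is confined to the descriptive HBs-alum PPS results at Day 361. It should be fixed before the final analysis, and it does not threaten the main analysis.

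**What to change.** Replace the third bullet of code 2090 in SAP Table 4 with two, using the protocol's own intervals:

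- Visit 7 to Visit 9 outside 286-314 days, for all groups except HBs-alum.
- Visit 8 to Visit 9 outside 166-194 days, for HBs-alum.

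Change the elimination program to match before the Day 361 analysis is run. The cost is one line of the SAP and the corresponding line of code. No main-analysis output changes. If the sponsor did intend the Visit 7 window for HBs-alum, SAP Section 4.8 should record it as a change from the protocol and justify it.
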